6.3.8 Cardiac MRI

LV structure and function as assessed by cardiac MRI include the following parameters:

- LV (myocardium) mass
- LV end-systolic volume
- LV end-systolic volume index
- LV end-diastolic volume
- LV end-diastolic volume index
- LV stroke volume
- LV ejection fraction
- systolic wall thickening (anterior LV, lateral LV, inferior LV, septal LV)
- regional wall motion [dyssynchrony index, circumferential uniformity ratio estimate (CURE)]
- circumferential strain (global, anterior LV, lateral LV, inferior LV, septal LV)
- LV wall thickness
 - end-systolic wall thickness average (anterior, lateral, inferior, septal)
 - end-diastolic wall thickness average (anterior, lateral, inferior, septal)

In addition, the LV mass index (g/m²) will be calculated as

$$\text{LV Mass Index (g/m}^2\text{)} = \text{LV Mass (g)}/\text{BSA (m}^2\text{)}$$

where Body Surface Area (BSA) = 0.007184 * Height (cm)^{0.725} * Weight (kg)^{0.425}. Height and weight measurements closest to the MRI scan will be used. The standing height will be used, if provided; otherwise, the height from ulna length will be used.

All observed values will be displayed in subject listings. Observed values and changes from baseline will be summarized for all parameters except LV wall thickness.

Using the model defined in Section 6.1, the comparisons of interest will be the contrasts between CAP-1002 and placebo at Months 6 and 12 for change from baseline in all parameters except LV wall thickness.

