2.2. Details of the Data Transformed Model

The primary efficacy analysis is change from baseline to Month 12 in the mid-level (elbow) dimension of the PUL 1.2 assessed via a parametric linear MMRM model to compare treatment groups in mean change from baseline to Month 12. If non-normality of the residuals is identified via the procedure identified in Section 2, a data transformation will be applied and then the primary MMRM model will be applied to the transformed data. This primary MMRM model on the transformed data tests the same hypotheses.

$$\begin{aligned} H_0: \mu_C - \mu_P &= 0 \\ H_a: \mu_C - \mu_P &\neq 0 \end{aligned}$$

where μ_C and μ_P are population mean of changes from baseline in CAP-1002- and placebo-treated subjects, respectively, which on the transformed data is also a test of the medians because the mean and the median of a distribution of percentiles are the same.

To implement this model, an MMRM analysis will be used to analyze the percentile ranked primary efficacy endpoint data using the same pre-specified ITT population. Data from the post-baseline visits (Month 3, 6, 9 and 12) will be modelled with visit, treatment, and treatment-by-visit interaction as the main effects, and ranked baseline score, site and binary stratification of entry item score of the PUL 1.2 at screening (2, 3 vs. 4, 5) as covariates. A First Order Autoregressive (AR(1)) covariance structure will be used to model the within-subject errors. The Kenward-Roger's (K-R) approximation will be used to estimate the denominator degrees of freedom. The primary comparison will be the contrast between CAP-1002 and placebo at Month 12.

For a given outcome, this analysis will be implemented by calculating the percentile rank of each change-from-baseline value relative to all observed change-from-baseline values for that outcome (across all subjects and all post-baseline observation times). The percentile ranked change-from-baseline is the dependent variable in the model.

This modeling approach will be applied to primary, secondary, and some exploratory endpoints for the ITT Population only.

In addition, for PUL and Cardiac MRI outcomes, Global Statistical Tests³ (GST) will be calculated as the averaged percentile ranked change-from-baseline.

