2.5. Data Visualization

Figures depicting model-adjusted least-squares means (LS-Means) by visit broken out by treatment arm will be produced for the primary, secondary, and some exploratory efficacy outcomes. This will apply to both raw and transformed outcome measures and their corresponding model estimates.

A forest plot will be produced for all PUL endpoints showing the magnitude, significance, and errors associated with several measures at Month 12 simultaneously. This plot will also include the GST of all PUL outcomes at Month 12. The same forest plot will be produced for Cardiac MRI outcomes, including the corresponding GST. Forest plots will only be produced for transformed outcome measures.

All figures will be produced for the ITT Population only.

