3.2. Cardiac and Steroid Medications

Frequencies and percentages of subjects reported or receiving WHODrug Global cardiac medications at any time on or after Day 1 (date of first IP exposure) will be both summarized by WHODrug Global Anatomic Therapeutic Chemical (ATC) Level 2 and Preferred Term and listed.

Frequencies and percentages of subjects reported or receiving WHODrug Global steroid medications at any time on or after Day 1 (date of first IP exposure) will be summarized separately for systemic use and non-systemic use, where steroid medications with reported

indications as DMD, DMD treatment, or SOC for DMD are considered for systemic use, and steroid medications with other indications are considered for non-systemic use. Both summaries will be presented by WHODrug Preferred Term. All steroid medications on study, along with their reported indications, will be listed.

4. Pharmacoeconomic Analysis

An exploratory analysis was planned to explore all-cause hospitalizations, hospitalizations for orthopedic injury/surgery or pulmonary infections, and antibiotic usage. Billing information was not to be collected; rather, standardized, composite or bundled costings of national averages was planned to be used in the analysis. Given the small sample size and minimal observations on trial, this analysis was not completed.

References

1. Siegel S. Nonparametric Statistics. Am Stat 1957;11(3):13–9.
2. Mallinckrodt CH. and Ilya Lipkovich. A practical guide to analyzing longitudinal clinical trial data. CRC Press. Boca Raton. 2017 (Chapter 11).
3. O'Brien PC. Procedures for comparing samples with multiple endpoints. Biometrics 1984; 40: 1079-87.

Signature Approval of SAP Addendum – Post Hoc Analysis HOPE-2 Study

A Phase 2, Randomized, Double-Blind, Placebo-Controlled Trial Evaluating the Safety and Efficacy of Intravenous Delivery of Allogeneic Cardiosphere-Derived Cells in Subjects with Duchenne Muscular Dystrophy (HOPE-2)

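### The cardiac MRI global test averages percentile ranks without orienting each outcome to benefit, so opposing outcomes offset and the summary can shrink, vanish or reverse

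*SAP*

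**What the plan says.** SAP Addendum 2.2 builds the transformed analysis by "calculating the percentile rank of each change-from-baseline value relative to all observed change-from-baseline values for that outcome", pooled over subjects and post-baseline visits. For the PUL and cardiac MRI families it then adds a GST that "will be calculated as the averaged percentile ranked change-from-baseline". Nothing in 2.2 reverses a rank, names a favourable direction or lists the components. A numbered reference is attached to the GST; the reference list gives its title as "Procedures for comparing samples with multiple endpoints", and the addendum text takes no alignment step from it.

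Addendum 2.5 describes a Month 12 forest plot of the PUL endpoints that carries a GST over all of them, and continues: "The same forest plot will be produced for Cardiac MRI outcomes, including the corresponding GST".

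The cardiac MRI outcomes are listed in SAP 6.3.8, which models treatment contrasts at Months 6 and 12 "for change from baseline in all parameters except LV wall thickness". The list holds "LV ejection fraction", stroke volume, four systolic wall thickening segments and the circumferential uniformity ratio estimate (CURE). It also holds "LV end-systolic volume", "LV end-systolic volume index", the end-diastolic volume and its index, a dyssynchrony index, five circumferential strain values, LV mass and a calculated LV mass index. Protocol 7.2.3 has a shorter list that also puts ejection fraction and stroke volume beside the two ventricular volumes.

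**The concern.** A larger raw change always receives a larger rank, whether a larger value of that outcome is good or bad. A mean of such ranks measures overall benefit only if every component runs the same way. The cardiac list does not. With the usual formula, ejection fraction = 1 - ESV/EDV (end-systolic over end-diastolic volume), so at a given EDV a fall in ESV raises ejection fraction. The same improvement then earns a high rank on one component and a low rank on the other, and the average cancels them. CURE and the dyssynchrony index form a similar pair, on the assumption that one rises and the other falls with improvement.

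The purpose of a global test is to give one direction for a family of outcomes. If the components are not oriented, its estimate and two-sided p-value cannot be read as evidence for or against benefit. Two analysts who settle the unstated points differently could report opposite signs. Because the addendum was written post hoc, an open orientation also leaves a choice that the data could influence.

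**Working it through.** **Nothing to reproduce.** The documents give no sample size, power or result for the GST.

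**Inputs from the documents.** 20 subjects randomised 1:1, taken as 10 per arm (SAP 3.1); two-sided tests at 0.05 (SAP 4); MRI at Months 6 and 12; ranks pooled over subjects and visits, then averaged (Addendum 2.2).

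**Assumptions.**
- Better when higher (7): stroke volume, ejection fraction, four wall thickening segments, CURE.
- Better when lower (5): the two ventricular volumes, their two indices, dyssynchrony index.
- Strain (5): either signed, with more negative better, or a magnitude, with higher better.
- Mass and mass index (2): left out, lower better, or higher better.
- The same standardised benefit on every component: 0.8 SD, varied to 0.5 and 1.0.
- Correlation between components on the benefit scale: 0.3, varied to 0 and 0.6. Correlation between visits: 0.6.

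**Step 1: shift of one aligned component.** With equal arms and pooled ranks, the expected difference in mean percentile rank is D = 100 x [Phi(d/√2) - 0.5]. For d = 0.8, D = 100 x (0.714 - 0.5) = 21.4 points.

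**Step 2: shift of the unaligned average.** With K components, unaligned difference = D x (up - down)/K.

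**Step 3: simulation.** 2,000 trials per setting. The Month 12 GST was compared by a two-sided t-test, a simplification of the addendum's repeated-measures model. Results for 0.8 SD and correlation 0.3:

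| Components averaged | Up/down | (up - down)/K | Step 2 | Simulated, unaligned | P(sig. benefit) | P(sig. harm) | Aligned: difference, power |
|---|---|---|---|---|---|---|---|
| SAP set, strain signed, mass out | 7/10 | -0.176 | -3.8 | -3.8 | 0.001 | 0.265 | +21.7, 0.828 |
| SAP set, strain signed, mass lower better | 7/12 | -0.263 | -5.6 | -5.6 | 0.001 | 0.460 | +21.4, 0.826 |
| SAP set, strain signed, mass higher better | 9/10 | -0.053 | -1.1 | -1.2 | 0.004 | 0.064 | +21.4, 0.834 |
| SAP set, strain magnitude, mass out | 12/5 | +0.412 | +8.8 | +8.8 | 0.625 | 0.000 | +21.4, 0.820 |
| SAP set, strain magnitude, mass lower better | 12/7 | +0.263 | +5.6 | +5.7 | 0.459 | 0.000 | +21.3, 0.829 |
| EF, SV, EDV, ESV only | 2/2 | 0 | 0 | +0.1 | 0.018 | 0.015 | +21.4, 0.682 |
| Those four plus one signed strain | 2/3 | -0.2 | -4.3 | -4.2 | 0.001 | 0.117 | +21.7, 0.715 |
| Those four plus one strain magnitude | 3/2 | +0.2 | +4.3 | +4.5 | 0.141 | 0.002 | +21.4, 0.705 |
| EF and four wall thickening segments | 5/0 | +1 | +21.4 | +21.1 | 0.702 | 0.000 | +21.1, 0.702 |

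Strain as a magnitude with mass higher better was not simulated; Step 2 gives 9/19 x 21.4 = +10.1.

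**Step 4: sensitivity, SAP set.**
- At 0.5 SD the unaligned difference is -0.8 to -3.6 with signed strain and +3.7 to +5.7 with strain as a magnitude.
- At 1.0 SD it is -1.4 to -6.9 and +6.8 to +10.6.
- Changing the correlation to 0 or 0.6 at 0.8 SD moves the unaligned difference by at most 0.2 points. Aligned power is 1.000 at correlation 0 and 0.55 to 0.58 at 0.6.
- With signed strain, the chance of a significant benefit never exceeds 0.009.

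**The case against.** The addendum is silent on orientation; it does not rule it out. Alignment may be intended through the cited method, and the list of final tables in SAP Appendix F is redacted. SAP 6.3.8 governs the individual contrasts, and the addendum does not say that all its parameters enter the GST. This limits the size of the claim. It does not remove it, because 2.2 gives a formula that can be run as it stands, and the parallel with the PUL plot in 2.5 suggests that the cardiac GST covers the whole family.

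A reader might infer that a cardiac benefit must cancel or appear as harm. The documents do not support that. Reversal on the SAP set needs signed strain, which is stated nowhere. With strain as a magnitude the sign stays right and 59% to 74% of the difference is lost (1 - 0.412 and 1 - 0.263). A same-direction set loses nothing.

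A reader might also take the GST as the main cardiac result. Addendum 2.5 only includes it beside the individual outcomes, whose directions would show in the same figure.

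The simulation is idealised. EF, SV, EDV and ESV are arithmetically linked, so equal shifts with equal correlations are a simplification. Ten per arm is a ceiling, since MRI is done only in subjects physically able to have it (Protocol 11.7). Misalignment does not by itself raise the false-positive rate when there is no effect.

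Finally, a reader might count overlapping components as part of the error: a volume with its index, or PUL dimensions with sums containing them. Overlap changes the weighting; it does not by itself invalidate a comparison of randomised arms, and no effect on the result has been shown. The PUL GST has no orientation problem: SAP 6.3.1 already adds the dimensions together, which presupposes a common direction.

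**Conclusion.** The point holds in a conditional form. As written, the cardiac GST averages ranks of raw change with no orientation step. Over the outcomes modelled in SAP 6.3.8, a consistent benefit partly or wholly offsets itself. Against an aligned difference of about +21 to +22 points (power 0.82 to 0.83 for 17 to 19 components), the simulated unaligned results are:

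- **Strain signed:** -1.2 to -5.6 points, with power for benefit below 0.01.
- **Strain a magnitude:** +5.7 to +8.8 points, with power 0.46 to 0.63.
- **EF, SV, EDV and ESV only:** about 0.
- **Same-direction outcomes only:** no loss.

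These figures rest on assumed directions, an equal 0.8 SD benefit on every component, correlation 0.3, 10 per arm and a t-test in place of the repeated-measures model. The ratio (up - down)/K does not depend on the effect size or the correlation.

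The consequence is limited. The addendum is declared post hoc, SAP 4.4 treats p-values after the interim analysis as nominal, and neither the primary endpoint nor the individual cardiac analyses are affected. The point should still be corrected, because the formula can give a misleading summary and the remedy costs almost nothing.

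**What to change.** In Addendum 2.2, add a table that lists every component of the cardiac MRI GST, its favourable direction and, for strain, the sign convention used by the imaging core. State that for each component where a lower or more negative value is improvement, 100 minus the percentile rank is used before averaging. Settle the directions on clinical grounds and without reference to the treatment results. If the GST has already been produced, rerun it with the table and label the forest plot row with its orientation.

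The cost is one table and one line of code, with no new data. Dropping overlapping components is optional and separate from this correction.

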2.3. Sensitivity Models

Several sensitivity models will be constructed to assess the robustness of the non-parametric model described above to other potential aspects of model misspecification. These analyses are described below and will only be performed for the primary endpoint in the ITT Population.

2.3.1. Permutation Test

Permutation tests at each analysis Visit (Month 3, 6, 9, and 12) will also be conducted as a non-parametric test for assessing robustness of the primary MMRM result. Permutation tests will be conducted by randomly sampling (without replacement) all possible permutations of the $N_{p,t}$ and $N_{T,t}$ values of the outcome variable, where $N_{p,t}$, $N_{T,t}$ are the number of subjects in placebo and treatment, respectively, at time t . The p-value is the proportion of permuted samples that have a test statistic larger than that of the observed data.

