3.1 Sample Size and Randomization

This trial will be limited to a total of 20 randomized subjects.

This is a double-blind, placebo-controlled trial. Subjects who meet all enrollment criteria will be prospectively randomized in stratified permuted blocks to CAP-1002 or placebo (1:1 ratio) via an interactive web-based response system (IWRS) accessed directly by site personnel who have been delegated this responsibility by the Principal Investigator (PI). Randomization will be stratified by site and entry item score of the PUL 1.2 at Screening (Stratum I: Score of 2 or 3; Stratum II: Score of 4 or 5). Subjects will be randomized approximately 7 days in advance of their first IP infusion (Day 1). The central randomization will be generated in SAS or comparable software using permuted random block sizes held in confidence by the statistician preparing the master randomization list.

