6.1 Primary Efficacy Endpoint

The primary efficacy endpoint is change from baseline to Month 12 in the mid-level (elbow) dimension of the PUL 1.2. The hypothesis set to be tested is:

$$H_0: \mu_c - \mu_p = 0$$

$$H_a: \mu_c - \mu_p \neq 0$$

where μ_c and μ_p are population mean absolute changes from baseline in CAP-1002- and placebo-treated patients, respectively.

A MMRM analysis will be used to analyze the primary efficacy endpoint using the ITT population. The results for Month 3, 6, 9 and 12 visits will be modeled with visit, treatment, and treatment-by-visit interaction as the main effects; baseline measurement, site and binary stratification of entry item score of the PUL 1.2 at screening (2, 3 vs. 4, 5) will be included as covariates in the model. An autoregressive (AR(1)) covariance structure will be the covariance structure to model within-subject errors. The Kenward-Roger's (K-R) approximation will be used to estimate the denominator degrees of freedom. The primary comparison will be the contrast between CAP-1002 and placebo at Month 12.

As a supportive analysis, the analysis may be evaluated in the PP population.

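### The Addendum's permutation test ignores the randomization strata, leaves its statistic undefined and counts in one direction only, so a null result would say little about the adjusted Month 12 contrast.

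*SAP*

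**What the plan says.** Addendum 2.3.1 adds permutation tests at Months 3, 6, 9 and 12, which "will also be conducted as a non-parametric test for assessing robustness of the primary MMRM result". On the mechanics: "Permutation tests will be conducted by randomly sampling (without replacement) all possible permutations of the" values in the two arms at that visit. On the p-value: "The p-value is the proportion of permuted samples that have a test statistic larger than that of the observed data". The section does not mention site, entry stratum, blocks or covariates, and it does not say what the test statistic is.

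SAP 3.1 describes the assignment. Subjects are "prospectively randomized in stratified permuted blocks to CAP-1002 or placebo (1:1 ratio"), the strata are site and PUL 1.2 entry item score (2-3 against 4-5), and the lists use "permuted random block sizes held in confidence by the statistician preparing the master randomization list".

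SAP 6.1 defines the result being checked: the Month 12 contrast from an MMRM whose covariates are "baseline measurement, site and binary stratification of entry item score of the PUL 1.2 at screening". SAP Section 4 makes all comparisons two-sided at 0.05 unless stated otherwise. SAP 4.4 treats every p-value after the interim analysis as nominal.

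**The concern.** A permutation test takes its justification from the way treatment was assigned. With permuted blocks, the arm imbalance in any site-by-stratum cell cannot exceed half the block size. The free shuffle has no such limit, so its reference set differs from the one the design generated. If the entry stratum predicts decline in PUL, the shuffle adds between-stratum variation that the randomization largely removed.

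Interpretation is also at stake. The Addendum's worry is non-normal residuals in 20 subjects. If the permutation test and the MMRM disagree, a reader cannot tell whether the cause is non-normality, lost stratification or, if the statistic is unadjusted, missing covariates. A non-significant permutation result could then be taken, wrongly, as a sign that the adjusted Month 12 result is fragile. In the other direction, a signed statistic with a one-directional count would be easier to pass than the SAP's two-sided rule.

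**Working it through.** The documents give no figure for this test (no number of permutations, p-value, size or power), so there is nothing of the plan's own to reproduce.

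**Inputs from the documents.** 20 randomized subjects (SAP 3.1), with arm sizes not stated. Two sites with one subject and three with one per arm (Addendum 2.3.2), that is 2×1 + 3×2 = 8 subjects. The layout of the other 20 − 8 = 12 is not given. Block sizes are not disclosed.

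**Assumptions.** The 12 placed as 4+4+4 or 6+6; blocks of 2 or 4; entry strata 50:50; effect sizes and covariate strengths as stated below; a single-visit adjusted contrast standing in for the MMRM.

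**Step 1: reference sets.**
- Free shuffle: C(20,10) = 184,756 for a 10/10 split; C(20,8) = 125,970 for 8/12.
- Within site only, larger sites balanced: 2³ × C(4,2)³ = 8 × 216 = 1,728 for 4+4+4; 2³ × C(6,3)² = 8 × 400 = 3,200 for 6+6. The one-subject sites contribute nothing.

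**Step 2: size at nominal 0.05, two-sided, difference in means** (1,000 trials, 499 permutations; Monte Carlo error √(0.05×0.95/1000) ≈ 0.007). Moderate and strong mean coefficients for site, stratum and baseline of 0.5, 1, 0.5 and 1, 2, 1 on a residual SD of 1.

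| Site, stratum, baseline | Free shuffle |
|---|---|
| Not prognostic | 0.045-0.051 |
| Moderate | 0.027-0.037 |
| Strong | 0.018-0.043 |

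Re-randomizing by the block scheme gave 0.044-0.059 over all these settings. The free shuffle is nominal to conservative and was never inflated.

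**Step 3: power at a 1.2 SD effect, sparse-site layout.**

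| Test | Stratum and baseline R² 20% each | Neither prognostic |
|---|---|---|
| Free shuffle, unadjusted | 69-73% | reference |
| Within entry strata, adjusted for baseline and stratum | 86-87% | about 3-7 points lower |
| Full site-by-stratum scheme, site also in the statistic | about 64-76% | about 12-26 points lower |

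The size of the within-strata test stayed near 5%. A smaller run (400 trials) gave 83-87% for the second row, and for the third 60-68% and a loss of 22-31 points. Site adjustment pays only when site itself is strongly prognostic: with the strong setting and a 1.5 residual-SD effect, power was 0.61-0.70 against 0.31-0.35 for the free shuffle.

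**Step 4: the p-value rule.** With a signed statistic, counting only larger values at 0.05 puts 0.05 in one tail, against 0.025 per tail under the two-sided rule. With nothing prognostic the simulated one-direction rate was 0.039-0.058. Ties matter too. On an outcome rounded to integers (moderate setting, absolute statistic, 2,000 trials) the strict count rejected in 0.043 of null trials, against 0.028 when ties and the observed arrangement are counted. On continuous outcomes the two counts gave identical rates. A strict count can also return p = 0.

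**The case against.** **The free shuffle is still useful.** It held its size or was conservative, and it needs no normality, which is what the Addendum set out to address. This stands. A reader might infer that the mismatch makes the p-value invalid or too small, or that the test says nothing about the MMRM. Neither follows: a small two-sided p-value remains evidence of a treatment difference at that visit. What is not checked is the adjusted Month 12 contrast.

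**Nothing says the statistic is unadjusted.** Correct. A reader might infer from the silence that covariates are excluded, but the supportable finding is only that the statistic is undefined. The free-shuffle figures above take it as a difference in means.

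**Matching the design fully could make matters worse.** This stands in part. With eight of 20 subjects at sparse sites, putting site in the statistic can cost more power than it gains. It would be wrong to assume that the full site-by-stratum scheme with the SAP 6.1 model brings the 86-87%, or costs only a few points.

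**Permuting within two entry strata is not the trial's exact scheme either.** True: it still ignores site and blocks. It is a compromise that held its size in the layouts tried.

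**Other checks exist.** The percentile-rank MMRM keeps baseline, site and stratum; Addendum 2.3.2 pools or removes site; 2.3.5 tries other transformations. All this limits the weight of the point. None of these is randomization-based.

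**Conclusion.** The point holds in a limited form. As written, the permutation is unrestricted although assignment was stratified and blocked, the statistic is undefined, and the p-value rule is one-directional unless the statistic is absolute, with ties uncounted. Section 4 allows exceptions to two-sided testing, but the Addendum does not declare one.

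The consequence is lost power and an ambiguous null result, not a false-positive problem, provided the test is made two-sided. The illustrative gain from the simpler fix is from about 69-73% to 86-87%. It depends on the assumed layouts, block sizes, 1.2 SD effect and R² values; none of these is in the documents, and the gain disappears if stratum and baseline do not predict outcome. The pre-specified primary analysis is unaffected. Priority is modest.

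**What to change.** Rewrite Addendum 2.3.1 to state:

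1. **Scheme.** Permute treatment labels within the two PUL entry-item strata, moving each subject's label for all visits together. State the number of permutations and the seed.
2. **Statistic.** The absolute Month 12 treatment contrast adjusted for baseline and entry stratum, without site because of the sparse sites in Addendum 2.3.2. Use the same form at Months 3, 6 and 9.
3. **P-value.** The proportion of arrangements with a statistic as large as or larger than the observed one, counting the observed arrangement itself.
4. **Optional further check.** Re-randomization from the master list's strata and blocks with the SAP 6.1 model including site, reported as additional and with its likely low power noted.
5. **Interpretation.** A non-significant result is not by itself evidence against the MMRM.

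Cost: some programming and computing time, and about 3-7 points of power if neither stratum nor baseline is prognostic. Adding site to the statistic would cost about 12-26 points in that case (up to about 31 in the smaller run), which is why it is left to the optional check.
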